10.2. Statistical analysis plan

The primary analysis will be based on an intention-to-treat population, including participants randomized. Similarly, safety analyses will be based a modified intent-to-treat population consisting of all participants who were randomized.

This is a controlled randomized trial testing a superiority hypothesis with a two-sided type I error rate of 0.05. Secondary hypotheses have been ordered according to relative importance. These will be described according to the appropriate summary statistics (e.g., proportions for categorical data, means with 95% confidence intervals for continuous data, median for time-to-event data).

A statistical analysis plan (SAP) will be prepared for analysis of primary and secondary outcomes and will include a plan for handling missing data.

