## 5 Study Methods

## 5.1 General Study Design and Plan

(ICH E3;9)

This is a multi-centre, randomised, double blind, placebo controlled, parallel group trial with two treatment arms, with 400 participants planned to be randomised

The two treatment arms are as follows:

[figure not shown]
- 1. Brensocatib 25mg once daily for 28 days
- 2. Placebo once daily for 28 days

Following trial completion or discontinuation, participants should be continued on standard of care.

Randomisation will be stratified by

- 1. Site
- 2. Age: <65 years/≥65 years

The proposed primary outcome assessed on a 7-point ordinal scale at day 28.

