## 5.3 Randomisation and Blinding

Participants will be allocated to receive either Brensocatib (25mg once daily for 28 days) or placebo in addition to standard of care. Randomisation will be 1:1 intervention:placebo. Randomisation will be stratified by site and age: <65 years/≥65 years. Randomisation will be done centrally using a web-based validated randomisation program provided by Tayside Clinical Trials Unit. The trial is doubled-blind, participants and trial staff are blind to allocation, unblinding will take place after database lockdown. Emergency unblinding procedures are described in section 7.6 of the protocol.

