#### 7.2.4 Safety Population

Safety analyses will be based a modified intent-to-treat population consisting of all participants who were randomised and received at least one dose of randomised therapy.

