## 10 Safety Analyses

Safety endpoints include cumulative incidence of SAEs, discontinuation or temporary suspension of treatment, changes in white cell count, haemoglobin, platelets, creatinine, total bilirubin, ALT and AST over time. Adverse events of special interest; hyperkeratosis (skin), infection, and dental complications will be reported. These events will be analysed univariately. The proportion of participants who had adverse events will compared between both the groups using Poisson regression. Adverse events leading to premature discontinuation from the study intervention and serious AEs will be presented either in a table or a listing.

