## 10.2 Adverse Events

For the calculation of incidence of adverse events (i.e., on a per subject basis), each subject will only be counted once and any repetitions of adverse events within a subject will be ignored; the denominator will be the number of subjects in the Treated population. All adverse events reported will be included in the summaries and analyses. Adverse events incidences will be reported by System Organ Class and Preferred Term.

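### The SAP compares the proportion of participants with an adverse event by Poisson regression and names no robust variance; with model-based errors the 95% interval is too wide

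*SAP*

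**What the plan says.** SAP section 10 (Safety Analyses) gives one between-arm method for adverse events: "The proportion of participants who had adverse events will compared between both the groups using Poisson regression". The sentence before it, which follows the list of events of special interest, reads "These events will be analysed univariately". No covariate is named for the comparison.

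SAP section 10.2 defines the quantity. For incidence, "each subject will only be counted once and any repetitions of adverse events within a subject will be ignored", and "the denominator will be the number of subjects in the Treated population". The outcome is therefore 0 or 1 for each participant, with participants as the denominator. No person-time offset is given. The safety population (SAP 7.2.4) is "all participants who were randomised and received at least one dose of randomised therapy".

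Shell Table 10 has a row for the percentage of patients with one or more adverse events and a column for the effect estimate with its 95% confidence interval. SAP 7.6 lists the same proportion, and the proportion with serious adverse events, among the preliminary analysis endpoints. SAP section 13 names the software package but no model options. Neither document names a robust variance, a log-binomial model or an exact method for this comparison. For another yes/no outcome, new mechanical ventilation, SAP 9.2.8 uses Fisher's exact test.

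**The concern.** Poisson regression is built for counts, whose variance equals the mean. A yes/no outcome with probability p has variance p(1-p), which is smaller. Fitted to a yes/no outcome, the model still estimates the risk ratio correctly, but its own standard errors are too large unless a robust variance is requested.

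At stake is the interval that Table 10 will print beside the adverse event risk ratio. If it is wider than the data warrant, a true excess of adverse events is more likely to be reported as inconclusive. In an efficacy comparison a conservative method is cautious. In a safety comparison it makes harm harder to detect.

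**Working it through.** **Inputs.** The design has "with 400 participants planned to be randomised" (SAP 5.1) and "Randomisation will be 1:1 intervention:placebo" (SAP 5.3), so about 200 per arm if nearly all are dosed. The confidence level is 95% (SAP 7.8). All adverse event rates below are assumptions, because the documents give none.

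**The plan's own figure.** There is no stated power or precision for adverse events. The only stated figure to check is the one behind the 400: about 85% power for an odds ratio of 1.75 on the ordinal scale. Whitehead's formula with the SAP Table 2 distribution gives N = 409.5 for 85% power, against 412 in SAP Table 3. At N = 400, z = sqrt((1.96 + 1.036)² × 400/409.5) - 1.96 = 1.00, which is 84.2% power. The 400 is reproduced.

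**Formulas.** With x events among n participants in each arm, the standard error of the log risk ratio is:

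- model-based Poisson: sqrt(1/x0 + 1/x1)
- binomial, which robust Poisson also gives here: sqrt(1/x0 - 1/n0 + 1/x1 - 1/n1)

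With equal arms and a common rate p, the ratio of the first to the second is 1/sqrt(1-p). It does not depend on n, so it is the same with 182 per arm (200 less the 9% loss to follow-up in SAP section 6).

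| Assumed rate in both arms | SE inflation |
|---|---|
| 5% | 1.03 |
| 10% | 1.05 |
| 20% | 1.12 |
| 30% | 1.20 |
| 40% | 1.29 |
| 50% | 1.41 |

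**Worked example, 40% versus 50%, 200 per arm.** Events are 80 and 100, the risk ratio is 1.25 and its log is 0.223.

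- Model-based: sqrt(1/80 + 1/100) = 0.150. The 95% CI is exp(0.223 ± 1.96 × 0.150) = 0.93 to 1.68.
- Correct: sqrt(0.6/80 + 0.5/100) = 0.112. The 95% CI is exp(0.223 ± 1.96 × 0.112) = 1.00 to 1.56.
- Chance that the interval excludes 1: (0.223 - 1.96 × 0.150)/0.112 = -0.63, or 26%, with model-based errors; 0.223/0.112 - 1.96 = 0.04, or 51%, with correct errors.

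**Check by fitting.** Fitted Poisson models with 80 versus 104 events (risk ratio 1.30) gave 0.97 to 1.74 (p = 0.078) with model-based errors and 1.05 to 1.61 (p = 0.017) with robust errors. With 10 versus 20 events (5% versus 10%) they gave 0.94 to 4.27 and 0.96 to 4.16, which are almost the same.

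**Check by simulation.** 200,000 trials per scenario, 200 per arm, no true difference:

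| Rate | Coverage of 95% CI, model-based | Coverage, robust | Interval excludes 1, model-based | Interval excludes 1, robust |
|---|---|---|---|---|
| 5% | 96.4% | 96.2% | 3.6% | 3.8% |
| 20% | 97.3% | 95.3% | 2.7% | 4.7% |
| 40% | 98.8% | 95.2% | 1.2% | 4.8% |
| 50% | 99.5% | 95.0% | 0.5% | 5.0% |

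At 5% both methods are slightly conservative, and they barely differ.

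**The case against.** The strongest reply is that the SAP does not specify model-based errors. It is silent, and Poisson regression on a proportion is often shorthand for the robust version. A reader might infer that the SAP has chosen the wrong errors; the text does not show that. If robust errors are intended, the problem disappears once this is stated. What stands is that the model as named, fitted with no further instruction, gives the wrong interval, and nothing in either document corrects it.

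The second reply concerns size. The effect is small for uncommon events. Protocol Appendix 1 expects hyperkeratosis to be rare and dental complications not to occur with short treatment. Protocol 9.2 keeps common COVID-19 symptoms, laboratory changes and non-fatal deterioration out of adverse event recording, which lowers the overall rate. This stands, and it is why the low rates are shown. It does not settle the matter for the any-event row, which pools everything reported; shell Table 13 lists more than 80 preferred terms.

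The third reply is that the documents set no hypothesis, power target or significance level for safety. The protocol's wording, "testing a superiority hypothesis with a two-sided type I error rate of 0.05", concerns the trial's superiority hypothesis, and safety also rests on unblinded data monitoring committee review, listings and laboratory grading. This too stands. The 26% and 51% above show lost precision, not a missed design target. Even with correct errors, a difference of 40% versus 50% would be missed about half the time.

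**Conclusion.** The point holds: wrong as written, in that the named model followed literally gives error bars that are too wide. The standard error is inflated by 3 to 5% at event rates of 5 to 10%, 12% at 20%, and 20 to 41% at 30 to 50%. This is negligible for rare events of special interest and material for any adverse event if that is common. It rests on two assumptions: that model-based errors would be used, since the SAP names no others, and the event rate, which the documents do not give.

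A reader might go further and infer that the method makes the drug look safer than the data show. The documents do not support that. The arm percentages and the risk ratio are unchanged, and the wider interval has the higher upper limit (1.68 against 1.56 in the example), so it rules out less harm. The loss is in the ability to show an excess. The primary endpoint is not affected.

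**What to change.** In SAP section 10, specify Poisson regression with robust (sandwich) standard errors, or log-binomial regression, and report the risk ratio with its 95% confidence interval. Keep the comparison univariate, as the section states; nothing here calls for covariate adjustment. With treatment as the only term, the two options give the same risk ratio and the same standard error, so the choice is one of convenience. Name one in advance.

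Use the same method for any between-arm comparison of the proportion with serious adverse events. Shell Table 10 leaves room for an effect estimate there and the SAP names no method for it. Apply it to these proportions in the preliminary analysis (SAP 7.6) as well, so that the two reports agree.

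The cost is one line of SAP text and one software option. No extra participants or data are needed.

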16. APPENDICIES

16.1. Appendix 1-Risk

Risks associated with trial interventions							
☐ A ≡ Comparable to the risk of standard medical care							
B ≡ Somewhat high	ner than the risk of standa	ard medical care					
☐ C ≡ Markedly highe	er than the risk of standar	d medical care					
month period in over 2 low risk of adverse effe	n investigational therapy b 200 patients with bronchie ects for 28 days treatmen	ectasis. The treatment t.					
Undesirable effects are	e detailed in section 6.3 o	of the IB					
What are the key risks interventions you plan	related to therapeutic to monitor in this trial?	How will these risks	s be minimised?				
IMP/Intervention	Body system/Hazard	Activity	Frequency	Comments			
Increase in severity of infections	Lung	Close monitoring	as clinically indicated	Not expected in view of phase 2 data			
Hyperkeratosis	Skin	Patients told to report	Daily while in hospital	Rare over 6 months in phase 2			
Dental complications	Teeth	Patients told to report	Daily while in hospital	Not expected with short treatment duration			
Neutropenia	Blood	Regular blood tests	as clinically indicated	Not observed in phase 2 study.			
Outline any other processes that have been put in place to mitigate risks to participant safety (e.g. DMC, independent data review, etc.)							
Participant safety will be reviewed periodically by the DMC.							
An information sheet will be provided for clinical staff caring for the participant detailing dosing instructions and possible adverse effects.							
Outline any processes (e.g. IMP labelling +/- accountability +/- trial-specific temperature monitoring) that have been simplified based on the risk adapted approach. Nil							

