## 9.2.8 Number of patients receiving new mechanical ventilation

The number and percentage of participants who received new mechanical ventilation will be presented. Comparison between the treatment arms will be performed using a Fisher's Exact test.

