## Oxygenation

No of days free from oxygen

Duration of new oxygen use

Mechanical ventilation

Number of patients receiving new mechanical ventilation

No of days free from ventilation

Duration of new ventilation used

Duration of hospital stay - days

28-day mortality

Table 10: Safety analyses

	Brensocatib N =	Placebo N =	Effect estimate (95% CI)
% of patients with at least 1 AE			
Incidence of SAEs			
Discontinuation or temporary suspension of treatment			
Changes in white cell count			
Changes in haemoglobin			
Changes in platelets			
Changes in creatinine			
Changes in total bilirubin			
Changes in ALT			
Changes in AST			
Adverse events, n (%):			
Hyperkeratosis (Skin)			
Infections			
Dental complications			

Table 11: Adverse Events

Adverse Event - n (%)	Brensocatib	Placebo
	N =	N =
Death		
Life-threatening		
Required hospitalisation		
Resulted in persistent or significant disability		
Medically significant		
Total		

Table 12: Summary of all adverse events - System Organ Class Level

N = N =	Total	Placebo	Brensocatib
	N=	N =	N =

Number of participants

Number of participants with adverse events

Number of participants without adverse events

Number of adverse events

Cardiac disorders

Eye disorders

Gastrointestinal disorders

General disorders and administration site conditions

Infections and infestations

Injury, poisoning and procedural complications

Investigations

Metabolism and nutrition disorders

Musculoskeletal and connective

tissue disorders

Nervous system disorders

No Code

Psychiatric disorders

Renal and urinary disorders

Respiratory, thoracic and mediastinal disorders

Skin and subcutaneous tissue

disorders

Vascular disorders

Table 13: Summary of all adverse events - Preferred Term Level

Brensocatib	Placebo	Total
N =	N =	N=

Number of participants

Number of participants with adverse

events

Number of participants without adverse

events

Number of adverse events

Abdominal discomfort

Abdominal pain

Acute kidney injury

Arthralgia

Back pain

Blood glucose increased

Bradycardia

Cerebrovascular accident

Chest discomfort

Chest pain

Clostridium difficile infection

Constipation

Cough

Delirium

Diarrhoea

Dizziness

Drug eruption

Dry mouth

Dry skin

Dysarthria

Dyspepsia

Dyspnoea

Dysuria

Electrocardiogram abnormal

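### If Poisson regression is used for the special-interest rows of SAP Table 10, its usual output breaks down when an arm has no events, and the SAP names no fallback

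*SAP*

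**What the plan says.** SAP section 10 singles out three kinds of event: "Adverse events of special interest; hyperkeratosis (skin), infection, and dental complications will be reported". Two short statements follow: "These events will be analysed univariately", and then "The proportion of participants who had adverse events will compared between both the groups using Poisson regression". No other method for comparing adverse events between arms is named. Nothing is said about the variance estimator, the form of test or interval, or what to do with sparse or empty cells. SAP 10.2 counts each participant once per event, so the data are binary.

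Table 10 in SAP section 16 has a row for the percentage "of patients with at least 1 AE" and separate rows for hyperkeratosis, infections and dental complications. All of them share one column for an effect estimate with 95% CI.

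On frequency, the risk table in Protocol Appendix 1 (16.1) says of hyperkeratosis "Rare over 6 months in phase 2" and of dental complications "Not expected with short treatment duration". It gives no rate for either.

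SAP 9.2.8, on new mechanical ventilation, has a method that copes with small counts: "Comparison between the treatment arms will be performed using a Fisher's Exact test". It is not assigned to adverse events.

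**The concern.** A Poisson model with treatment as the only term estimates the log of the ratio of the two observed risks. If one arm has no events, that log ratio has no finite maximum-likelihood estimate. The software stops wherever its iterations end, the model-based standard error is enormous, and the Wald p-value is close to 1 whatever the other arm shows. If neither arm has an event, nothing can be fitted.

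The pattern a safety comparison most needs to handle is a set of events all on the active drug. For the risks the trial chose to watch, that is where the usual output of the one named method is least informative. The SAP has no fallback, so the analyst would have to choose one after seeing the counts.

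**Working it through.** **Inputs.** 400 participants planned, 1:1 allocation (SAP 5.1 and 5.3), so about 200 per arm; two-sided 5% level (Protocol 10.2); adverse events recorded from consent to day 29 (Protocol 9.3). No adverse-event rate is given anywhere, so every rate below is an assumption.

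**1. The plan's own figure.** The only related figure is the basis for 400 participants. With the Whitehead formula, N = 12(z₁₋α/₂ + z₁₋β)² / {[ln OR]² (1 − Σp̄³)}, and the control distribution in Protocol Table 4, an odds ratio of 1.75 at 85% power needs 409.5 (stated: 412). With 400 participants, power is 84.2% (stated: about 85%). This reproduces, so 200 per arm is a sound working size.

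**2. How often an arm is empty.** Let q = (1 − p)²⁰⁰ be the chance of no event in one arm. With equal risk p in both arms, the chance that at least one arm is empty is 1 − (1 − q)², and the chance that both are is q².

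| Assumed 28-day risk | q | At least one arm empty | Both arms empty |
|---|---|---|---|
| 0.1% | 0.819 | 97% | 67% |
| 0.5% | 0.367 | 60% | 13% |
| 1% | 0.134 | 25% | 1.8% |
| 2% | 0.018 | 3.5% | about 0 |

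The chance of at least one empty arm passes 50% only below a risk of about 0.61% per arm. With unequal risks of 0.5% and 2% it is 38%.

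The hyperkeratosis comment refers to 6 months. If a 6-month risk r is scaled to 28 days at constant hazard (an assumption), p = 1 − (1 − r)^(28/182.5). Values of r of 1%, 2%, 4% and 10% then give a 93%, 79%, 49% and 8% chance of at least one empty arm.

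**3. What the model returns for 6/200 against 0/200.** The fit stops at a log ratio of about 22.4 (ratio about 5 × 10⁹). That value and its standard error depend on where the iterations end and will differ between packages.

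| Inference | Result |
|---|---|
| Wald, model-based SE 17,985 | p = 0.999 |
| Wald, robust SE 0.40 | p prints as 0 |
| Likelihood ratio, χ² = 2 × 6 × ln 2 = 8.32 | p = 0.004 |
| Exact conditional Poisson, 2 × 0.5⁶ | p = 0.031; ratio at least 1.18, no upper limit |
| Fisher's exact test | p = 0.030 |

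The lower limit of 1.18 is 0.025^(1/6) / (1 − 0.025^(1/6)) = 0.541 / 0.459.

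**4. Risk difference with Newcombe interval, same data.** The Wilson limits are 1.38% and 6.39% for 6/200, and 0 and 1.88% for 0/200.

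Lower limit: 3.0% − √[(3.0 − 1.38)² + 1.88²]% = 0.5%.
Upper limit: 3.0% + (6.39 − 3.0)% = 6.4%.

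Other splits, 200 per arm:

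| Events | Risk difference (95% CI) | Fisher p |
|---|---|---|
| 0 v 0 | 0% (−1.9% to 1.9%) | 1 |
| 3 v 0 | 1.5% (−0.6% to 4.3%) | 0.248 |
| 5 v 0 | 2.5% (0.1% to 5.7%) | 0.061 |
| 6 v 0 | 3.0% (0.5% to 6.4%) | 0.030 |

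All are finite, including the row with no events, where the Poisson fit fails.

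**The case against.** **The Poisson sentence may not cover these rows.** It speaks of the proportion of participants with adverse events, which fits the any-event row best, and an empty arm there is implausible. The three special-interest events have their own sentences, with no model named. This stands: applying Poisson regression to each event is a reading of Table 10's shared effect column, not a stated instruction. If that reading is wrong, Table 10 asks for three estimates with no method behind them, and the same added sentence closes the gap.

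**Empty arms may not occur.** A reader might infer that they are likely for two of the three events. The documents do not support that. Appendix 1 offers words and no rates, and step 2 runs from 97% to 3.5% over modest assumptions. The dental comment sits in a table of intervention risks and does not say that dental events will be absent on placebo. The SAP's preferred-term shell (Table 13) lists toothache, gingival pain and gingival bleeding. Foreseeable, mainly for hyperkeratosis, is as far as the text goes.

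**Poisson regression is not useless here.** A reader might also infer that it can yield nothing with an empty arm. The failure belongs to Wald inference: the exact conditional result for 6 v 0 (p = 0.031) nearly matches Fisher's. The robust p-value near 0 likewise depends on a variance that the SAP never names. Both points stand. But the SAP names no alternative to Wald output, and step 3 shows the answer moving from 0.999 to about 0 with that unstated choice.

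**The example is favourable.** Six against zero is the smallest such split at which Fisher's test falls below 0.05. With very rare events, smaller splits or none at all are more probable, and the counts then carry most of the information. This stands, and it limits the harm.

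**Conclusion.** The point holds as a minor gap. For the three special-interest rows of Table 10, the SAP either relies on a method whose standard output fails with an empty arm or names no method at all.

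The size rests on 200 per arm, equal risks and assumed rates; none of the probabilities can be read off the documents. The consequences are bounded. The counts per arm will be reported whatever the model does, the DMC reviews unblinded safety data, and no stated decision depends on a safety p-value. It would go too far to conclude that a real excess on brensocatib would be hidden.

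**What to change.** Add to SAP section 10 that hyperkeratosis, infections and dental complications in Table 10 are each compared by the difference in risk between arms, with a Newcombe 95% CI (or Miettinen-Nurminen; choose one in advance), and by Fisher's exact test, as SAP 9.2.8 already does for new mechanical ventilation. Label the effect column for those rows as a risk difference. Keep Poisson regression for the row on participants with at least one adverse event.

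Do not extend the rule to every sparse category. The tables by system organ class and preferred term have no effect column, and serious events are to be tabulated or listed. Adding tests there would create many comparisons that the SAP leaves descriptive.

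The cost is one sentence and a column label. The three rows would report an unadjusted risk difference rather than a ratio; SAP section 10 plans no covariate adjustment for these events, so little is lost. The interval and the test can disagree at the margin: for 5 v 0 the interval excludes zero while Fisher's p is 0.061. The SAP should therefore say that the interval is the estimate to be read.
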